5.2.3 Corticosteroid Requirement Changes over Time

Systemic corticosteroid therapy for cGVHD will be monitored throughout the study. The corticosteroid dose level will be measured by the daily dose amount versus the weight of subject (mg/kg/day). For the days without weight measurement, the last observed weight measurement will be used. Considering the frequency of corticosteroid use might not be once daily, we use weekly average daily dose instead of the actual daily dose. The average corticosteroid dose level in each week is calculated by

$$\text{Sum of total corticosteroid dose used in this week} / 7$$

If a subject terminated the study drug in the middle of the week, the average corticosteroid dose level in that week will be calculated by

$$\text{Sum of total corticosteroid dose used in the week before the study drug termination} / \text{actual days in the week up to the last dose of study drug.}$$

Evaluation of systemic use of corticosteroid therapy will be performed for those subjects with SD or PD as their best overall response, and separately for subject with a best overall response of PR or CR.

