5.3.3. Management of Steroids

Systemic steroids may be decreased at the treating physician's discretion. The initial taper of steroids may begin two weeks following initiation of ibrutinib if a clinical response is seen. The recommendation is to not taper below 50 percent of the original dose by the 12-week assessment period unless there is a documented medical reason for steroid reduction below 50 percent (eg, uncontrolled diabetes, infection). A specific steroid taper schedule will not be mandated.

Because cGVHD by its nature is a protean disease with clinical manifestations that wax and wane over time, closely spaced clinical evaluations will detect temporary exacerbations of cGVHD manifestations but may not accurately reflect the long term trajectory of a subject's cGVHD and response to treatment. Therefore, in the event a participant experiences a flare of cGVHD, a temporary increase in steroids will be allowed until symptoms return to baseline or criteria are met for progressive cGVHD. If criteria are met for progressive cGVHD, the participant will be scored as a treatment failure and removed from the study.

Non-absorbable oral steroids will be allowed and recorded.

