4.7 Extent of Study drug Exposure

The exposure to study drugs will be summarized. The following parameters will be summarized when applicable:

- Duration of treatment
- Cumulative dose received on study
- Dose intensity
- Relative dose intensity
- Dose reduction due to AE
- Dose interruption with 7 days or more due to AE

5. Efficacy Analysis

Unless specified otherwise, all information from the Phase 1b and Phase 2 parts of the study will be combined for efficacy analysis. The primary population used to evaluate efficacy is All Treated Population and where applicable, the response evaluable analysis set will be used as a sensitivity analysis to assess the robustness of the results.

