5.2.4 Change in Lee cGVHD Symptom Scale

Subject-reported improvement in symptom burden will be evaluated. The symptom burden is measured according to the Lee cGVHD Symptom Scale ([Lee 2002](#)). There are 7 domains, and each has several items.

Subscale	Related Items	Maximum number of missing items to get a valid score
Skin	1, 2, 3, 4, 5	2
Energy	14, 21, 22, 23, 24, 25, 26	3
Lung	12, 13, 15, 16, 27	2
Eye	6, 7, 8	1
Nutrition	11, 17, 18, 19, 20	2
Mouth	9, 10	1
Psychological	28, 29, 30	1

A score is calculated for each subscale by taking the mean of all items completed if more than 50% were answered and normalizing to a 0 to 100 scale. A total summary score is calculated as the average of these 7 subscales if at least 4 subscales have valid scores. The SAS code copied from Lee's website for the calculation is in [Appendix 8.2](#). A summary of total scores as well as each subscale scores for Lee cGVHD symptom scale will be performed throughout the study.

A change in >7 points on the Lee cGVHD Symptom Scale will be considered significant and relates to improvement in quality of life ([Lee 2006](#)). A summary of the proportion of subjects who have decreases of at least 7 points in Lee cGVHD symptom scale during the study will be performed.

Evaluation of Lee cGVHD Symptom Scale will be performed for those subjects with SD or PD as their best overall response, and separately for subject with a best overall response of PR or CR.

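### SAP 5.2.3 specifies the corticosteroid evaluation only within best-response groups and leaves weeks after the last ibrutinib dose undefined, so it names no all-treated change in steroid dose

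*SAP*

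**What the plan says.** **Steroid endpoint.** SAP 5.2.3 defines a weekly average dose in mg/kg/day. The evaluation it then names is split by best overall response: "Evaluation of systemic use of corticosteroid therapy will be performed for those subjects with SD or PD as their best overall response". PR/CR subjects form the second group, evaluated apart from the first. The section names no pooled group, comparison week or change statistic.

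**Stopping ibrutinib.** The section states that "Systemic corticosteroid therapy for cGVHD will be monitored throughout the study". Its one rule for discontinuation begins "If a subject terminated the study drug in the middle of the week" and divides the dose taken before termination by the "actual days in the week up to the last dose of study drug". Later weeks are not mentioned.

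**General rules.** SAP section 5 (Efficacy Analysis) says: "The primary population used to evaluate efficacy is All Treated Population". SAP 3.1.3 defines change from baseline within subject. SAP 3.3 does not impute missing efficacy data unless otherwise specified. SAP 5.2 plans descriptive statistics and no test for this endpoint.

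**Conduct and interpretation.** Protocol 5.3.3 says: "The initial taper of steroids may begin two weeks following initiation of ibrutinib if a clinical response is seen". It also lets the treating physician reduce steroids at discretion, permits a temporary increase on flare, and removes subjects who meet progression criteria as treatment failures. Protocol 10.2.2.3 treats a lower steroid need as benefit of ibrutinib, and SAP 3.3.2 says average daily steroid use serves to evaluate the treatment effect.

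**Symptom scale.** SAP 5.2.4 plans a summary of total and subscale scores over the study and the proportion with a decrease of at least 7 points. Neither is restricted by response. A further evaluation "will be performed for those subjects with SD or PD as their best overall response"; PR/CR subjects are again a second group.

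**The concern.** The trial has no control arm, so a claim of steroid sparing rests on which subjects and which weeks enter the summary. As written, 5.2.3 leaves three openings.

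- **Grouping on a post-baseline outcome.** Best response is known only after treatment starts, and the initial taper is itself tied to response. A fall in dose among PR/CR subjects is therefore partly built in, and neither group describes all treated subjects.
- **Subjects in neither group.** A treated subject with no evaluable post-baseline response is neither SD/PD nor PR/CR. The SAP allows for this possibility, since section 5 keeps a response-evaluable set apart from the All Treated Population.
- **On-drug data.** If summaries stop at the last ibrutinib dose, subjects whose steroids rose on a flare and who then progressed leave the average, and their later doses go uncounted.

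At stake is the reading of a declared secondary endpoint. No hypothesis test depends on it.

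**Working it through.** The documents give no dropout rate, dose spread or expected change for this endpoint, so there is no plan figure to reproduce. The check has a textual part and an illustrative part.

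**1. Steroids against symptom scale.** In 5.2.4 two unsplit summaries precede the response split. In 5.2.3 the split stands alone. The gap is specific to steroids.

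**2. What steroid data exist after the last dose.** Medications are recorded to 30 days after the last dose (protocol 7.1.5). Steroid requirements are reviewed at the Progressive Disease and End-of-Treatment visits (8.2.1, 8.2.2). They are also reviewed at 12-weekly response follow-up visits for subjects who stopped for other reasons, until progression (8.3.1). After progression, follow-up is for survival (8.3.2), and Appendix A schedules no steroid assessment there. Post-drug data therefore exist, but not for late weeks in early progressors.

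**3. Unpaired means.** Assumed: log-normal baseline dose, median 0.3 mg/kg/day, log-SD 0.5; no subject's dose ever changes; a logistic model for staying; 400,000 simulated subjects. The mean dose of those remaining is compared with the baseline mean of everyone:

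| Log-odds of leaving per SD of dose | 70% retained | 50% retained |
|---|---|---|
| 0 | 0% | 0% |
| 0.5 (odds ratio e^0.5 = 1.65) | -7.5% | -11.8% |
| 1.0 (odds ratio e^1.0 = 2.72) | -13.4% | -20.4% |

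With the within-subject change of SAP 3.1.3, every cell is exactly 0%, because post-baseline minus baseline is zero for each subject.

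**4. Paired change when dose varies.** Assumed: 40 subjects; weekly log-dose steps with SD 0.05 and mean -0.05²/2, so the expected ratio to own baseline stays 1; 50% responders; 1% weekly discontinuation, raised to 5% or 10% while dose is more than 25% above baseline. Change is each subject's ratio to own baseline, minus 1.

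| Scenario | Week 24 | Week 48 |
|---|---|---|
| Response split only, correlation 0.3 to 0.6 between response and dose fall: PR/CR | -5.0% to -11.1% | -4.9% to -11.5% |
| Same: SD/PD | +6.7% to +12.3% | +7.3% to +12.3% |
| Dose-related exit only, everyone still on drug | -2.5% to -4.9% | -8.7% to -13.2% |
| Both: PR/CR on drug | -7.4% to -12.6% | -11.9% to -17.8% |
| Doses of all 40 kept after exit | about 0% | about 0% |

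With weekly SD 0.10, the last week-48 PR/CR range becomes -27.8% to -38.1%. The split alone moves the two groups in opposite directions and leaves the pooled mean near zero. Restriction to on-drug data shifts the pooled mean, and pairing does not remove that shift.

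**5. Calendar for a fixed-week summary.** SAP 3.4 counts an efficacy month as 28 days. Six months is 6 × 28 = 168 days and twelve is 12 × 28 = 336 days, next to the Week 25 and Week 49 target days of 169 and 337 in SAP 8.1.

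**The case against.** The best defence is that nothing is excluded. SAP section 5 makes the All Treated Population primary for efficacy, the protocol synopsis plans efficacy analyses on all RP2D subjects, and protocol 10.4 plans a descriptive summary of steroid changes. A by-response table is an ordinary display. This stands to the extent that a pooled steroid summary is unspecified rather than forbidden. It does not settle the matter, because 5.2.3 is the specific section and names only the split.

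Several stronger readings are tempting and are not supported:

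- **That the symptom scale has the same defect.** It does not; 5.2.4 already plans two summaries not split by response.
- **That the SAP discards steroid data after the last dose.** The formula covers one partial week, and the section also speaks of monitoring throughout the study. Truncation is implied, not stated.
- **That a spurious fall of 7.5% to 20% should be expected.** Those figures need unpaired means, which SAP 3.1.3 does not define, and every input is assumed.
- **That tapering is wholly determined by response.** Protocol 5.3.3 also allows physician discretion and mandates no schedule.
- **That a complete all-treated dose summary needs only existing data.** Steroid data largely end once a subject progresses.

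It is also fair that protocol 7.2.3 already plans failure-free survival with corticosteroid requirements at 6 and 12 months, which comes close to an all-treated composite. SAP 5.3 does not carry the steroid part forward.

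**Conclusion.** The point holds for corticosteroids. The only evaluation that 5.2.3 specifies conditions on post-baseline response, omits subjects with no evaluable response, and leaves weeks after the last study dose open to two readings. With the initial taper tied to response and progressing subjects removed, the resulting summaries do not estimate the change in all treated subjects, and on-drug summaries can favour ibrutinib.

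The direction rests on one assumption, that subjects whose steroid dose rises are more likely to leave; the flare and progression rules make this plausible. The size cannot be estimated from the documents, and the simulated percentages illustrate the mechanism without predicting this trial's results. If leaving is unrelated to dose, the on-drug restriction introduces no bias, though the response split still does not describe the whole group. Because the endpoint is descriptive and untested, no error rate or power statement changes. It should be fixed because the protocol reads a fall as benefit.

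**What to change.** In SAP 5.2.3:

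1. Make the main analysis an All Treated summary of within-subject change from baseline in weekly average steroid dose, as defined in SAP 3.1.3, at fixed weeks such as 13, 25 and 49. Report the number contributing at each.
2. State that steroid data collected after the last study dose are used where available: the 30-day medication record and the Progressive Disease, End-of-Treatment and response follow-up visits.
3. Add the proportion of all treated subjects who, at 6 and 12 months, are alive, without progression, malignancy relapse or new systemic cGVHD therapy, and below their baseline steroid dose. Count everyone else, including those with missing data, as not achieving it. This handles the absence of steroid data in survival follow-up and extends the measure in protocol 7.2.3.
4. Label the by-response tables in 5.2.3 and 5.2.4 as supportive. No other change to 5.2.4 is needed.

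The cost is a few sentences and tables, with no new data collection. The headline steroid reduction may look less favourable, and counting missing data as failure makes the proportion conservative.

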5.2.4 Change in Lee cGVHD Symptom Scale

Subject-reported improvement in symptom burden will be evaluated. The symptom burden is measured according to the Lee cGVHD Symptom Scale ([Lee 2002](#)). There are 7 domains, and each has several items.

Subscale	Related Items	Maximum number of missing items to get a valid score
Skin	1, 2, 3, 4, 5	2
Energy	14, 21, 22, 23, 24, 25, 26	3
Lung	12, 13, 15, 16, 27	2
Eye	6, 7, 8	1
Nutrition	11, 17, 18, 19, 20	2
Mouth	9, 10	1
Psychological	28, 29, 30	1

A score is calculated for each subscale by taking the mean of all items completed if more than 50% were answered and normalizing to a 0 to 100 scale. A total summary score is calculated as the average of these 7 subscales if at least 4 subscales have valid scores. The SAS code copied from Lee's website for the calculation is in [Appendix 8.2](#). A summary of total scores as well as each subscale scores for Lee cGVHD symptom scale will be performed throughout the study.

A change in >7 points on the Lee cGVHD Symptom Scale will be considered significant and relates to improvement in quality of life ([Lee 2006](#)). A summary of the proportion of subjects who have decreases of at least 7 points in Lee cGVHD symptom scale during the study will be performed.

Evaluation of Lee cGVHD Symptom Scale will be performed for those subjects with SD or PD as their best overall response, and separately for subject with a best overall response of PR or CR.

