- Review adverse events and concomitant medications (including corticosteroid requirements)
- Pharmacokinetic sampling for PCYC (pre-dose)
- Pharmacodynamic sampling for PCYC (pre-dose)
- T/B/NK sampling for PCYC (pre-dose before Day 2 drug administration)

During and Post Dose

- Administer ibrutinib at specified dose level
- Pharmacokinetic sampling for PCYC at 1, 2, 4, and 6 hours post-dose
- Pharmacodynamic sampling for PCYC (4 hours after first dose administration)
- T/B/NK sampling for PCYC (4 hours after drug administration)

Week 5, 9, 13, 17, 21, 25 (\pm 3 days)**Predose**

- DLT assessment period ends (Phase 1b Week 5 only)
- Symptom-directed physical examination
- Vital signs and performance status (KPS)
- Photographic imaging of cGVHD (Weeks 5, 13 and 25)
- Hematology
- Serum chemistry
- cGVHD assessment per NIH (Weeks 5, 13 and 25) ([Appendix F](#) and [Appendix G](#))
- Lee cGVHD Symptom Scale (Weeks 5, 13 and 25) ([Appendix E](#))
- Donor/host chimerism testing (Weeks 13 and 25)
- Quantitative serum immunoglobulins (IgA, IgG, and IgM) (Weeks 13 and 25)
- Biomarker sampling (Weeks 5, 12 and 25)
- Pharmacodynamic sampling for PCYC (pre-dose on Weeks 9 and 13)
- T/B/NK sampling for PCYC (pre-dose on Weeks 9 and 13)
- Immunosuppressant level – if applicable
- Review returned subject dosing diary
- Review adverse events and concomitant medications (including corticosteroid requirements)

Post Dose

- Administer ibrutinib at specified dose level, and then dispense remaining amount to subject
- Pharmacodynamic sample collection (4 hours after drug administration on Weeks 9 and 13)
- T/B/NK sampling for PCYC (4 hours after drug administration on Weeks 9 and 13)

Week 37 and every 12 weeks thereafter**Predose**

- Complete physical examination
- Vital signs and performance status (KPS)
- Photographic imaging of cGVHD
- Hematology
- Serum chemistry
- cGVHD assessment per NIH ([Appendix F](#) and [Appendix G](#))
- Lee cGVHD Symptom Scale ([Appendix E](#))
- Donor/host chimerism testing
- Quantitative serum immunoglobulins (IgA, IgG, and IgM)
- Biomarker sampling (Weeks 37 and 49)

- Immunosuppressant level – if applicable
- Review returned subject dosing diary
- Review adverse events and concomitant medications (including corticosteroid requirements)

Post Dose

- Administer ibrutinib at specified dose level, and then dispense remaining amount to subject

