8.3.1. Response Follow-up

Subjects who discontinue the study for reasons other than progressive disease will be followed every 12 weeks (± 7 days) by clinic visit until progressive disease. During this period, the following procedures will be performed:

- Symptom-directed physical examination
- Vital signs and performance status (KPS)
- Hematology
- Serum chemistry
- Donor/host chimerism testing cGVHD NIH Form assessment ([Appendix F](#) and [Appendix G](#))
- Lee cGVHD Symptom Scale ([Appendix E](#))
- Photographic imaging of cGVHD
- Review corticosteroid requirements and any new cGVHD treatment if applicable

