3.1.2 Baseline Value

Unless otherwise specified, the baseline value is defined as the last valid measurement on or prior to the first dose of study drug

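### The Lee symptom-scale responder proportion names no visit and no confirmation rule, so measurement noise pushes it upward and it grows with the number of questionnaires.

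*SAP*

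**What the plan says.** SAP 5.2.4 builds the score from seven subscales, each normalised to 0–100: "A total summary score is calculated as the average of these 7 subscales if at least 4 subscales have valid scores". It then gives the threshold: "A change in >7 points on the Lee cGVHD Symptom Scale will be considered significant". The next sentence plans "A summary of the proportion of subjects who have decreases of at least 7 points", and the period attached to the count is the whole study: "decreases of at least 7 points in Lee cGVHD symptom scale during the study". No visit, window or confirmation rule is attached to that count, and nothing says how scores after drug discontinuation or after new cGVHD treatment are handled. The section does not say whether the rule applies to the total or to each subscale, and no count of worsening is planned. Results are to be shown separately for subjects whose best response is PR or CR and for those whose best response is SD or PD.

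Under SAP 3.1.2, "the baseline value is defined as the last valid measurement on or prior to the first dose of study drug", so baseline is one score and not an average.

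Protocol 8.2 schedules "Lee cGVHD Symptom Scale (Weeks 5, 13 and 25" and then lists the scale again under "Week 37 and every 12 weeks thereafter". Protocol 8.2.1 and 8.2.2 add it at the progressive-disease and end-of-treatment visits. Protocol 8.3.1 adds it after treatment: "Subjects who discontinue the study for reasons other than progressive disease will be followed every 12 weeks". Once a subject has progressed, Protocol 8.3.2 collects survival only. Protocol section 10 sets the analysis at about 12 months after the last subject's first dose, and Protocol 5.1 confirms an open-label study without randomisation.

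**The concern.** A rule that credits a subject for one low score among several compares the best of many noisy measurements with one noisy baseline. A subject whose condition never changes gets a new chance to qualify at every visit, and later scores near baseline do not remove the credit. The matching upward excursions are not counted.

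Three features make this matter here. First, there is no control group whose any-time rate would show how much of the proportion is noise. Second, the number of looks varies between subjects. If SD/PD subjects leave assessment earlier, they have fewer chances to qualify, and the split by best response could show a link between response and symptom benefit that follow-up alone created. Third, Protocol 5.3.3 itself describes cGVHD as fluctuating and warns that closely spaced evaluations can mislead about its long-term course. An any-time count credits exactly those temporary dips.

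At stake is how a named secondary objective is read. A responder percentage tied to quality of life is easily quoted alone.

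**Working it through.** The documents give no expected rate, SD or power for the Lee scale, so there is no planned figure to reproduce.

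**Inputs from the documents.** Threshold: a decrease of 7 (SAP 5.2.4). Baseline: one score (SAP 3.1.2). Post-baseline looks by Week 49: Weeks 5, 13, 25, 37 and 49, so K = 5 (Protocol 8.2). About 40 subjects at the RP2D (SAP 1.2).

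**Assumptions.** The true score is constant. Each observed score carries a normal error with SD s. The documents do not give s, so a range is shown. Errors are independent at first, then correlated.

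**One fixed visit.** The difference of two scores has SD s√2, so P = Φ(−7/(s√2)). For s = 5 this is Φ(−7/7.07) = Φ(−0.99) = 16%.

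**Any of K visits.** Given the baseline error Z in SD units, each visit qualifies with probability Φ(Z − 7/s). Hence P = 1 − E[(1 − Φ(Z − 7/s))^K], by numerical integration. Two consecutive qualifying visits are by simulation.

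| s | One fixed visit | Any of 5 | Two consecutive of 5 |
|---|---|---|---|
| 2 | 1% | 3% | 0.2% |
| 3 | 5% | 16% | 3% |
| 5 | 16% | 42% | 14.5% |
| 7 | 24% | 55% | 24% |

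At s = 5 in 40 subjects, that is 40 × 0.42 ≈ 17 apparent improvers against 40 × 0.16 ≈ 6. By symmetry, the same share would show an any-time increase of 7.

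**Dependence on the number of looks (s = 5).** 2 looks: 26%. 3 looks: 33%. 5 looks: 42%. 9 looks: 53%. If one group averaged two looks and the other five, noise alone would separate them by about 42 − 26 = 16 percentage points.

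**Correlated errors.** With AR(1) errors and s = 5, any of 5 visits against Week 25 alone is 38% vs 16% (correlation 0.3), 33% vs 14.5% (0.5) and 25% vs 11% (0.7). At correlation 0.7 the any-time rate is 16% for s = 4 and 39% for s = 7. The inflation shrinks but does not vanish.

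**The two thresholds.** With every item answered, a change in total is (25/7)(a/5 + b/7 + c/3 + d/2) for integers a to d. Setting this to 7 requires the bracket to equal 1.96, which is 411.6 in units of 1/210. That is not an integer, so a change of exactly 7 cannot occur, and strictly more than 7 gives the same count as 7 or more. The wording should still be made consistent.

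**Total or subscale.** A one-step change in one of the two mouth items moves the mouth subscale by 25/2 = 12.5 points but the total by only 12.5/7 ≈ 1.8. The rule therefore means very different things on the two scores.

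**The case against.** The case on the other side has substance.

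- *The any-time rule is inferred.* The SAP never says that any one questionnaire suffices, and SAP 3.2 and 8.1 do supply by-visit rules and windows. This stands as a caution. Any-time remains the natural reading because no visit is attached to the count, and if another rule was meant it is not stated.
- *The size depends on an assumed SD.* This stands. A total averaged over seven subscales may have a small error SD, and at SD 2 the any-time rate is only about 3%. Early progression also reduces the number of looks for some subjects, while long follow-up adds looks for others. A reader might take 31–55% (SD 4 to 7, independent errors) as the expected inflation. The documents do not support that.
- *The endpoint is descriptive.* This stands. SAP 5.2 formally tests only the primary endpoint and sustained response. A reader might infer that a trial conclusion or the type I error is at risk, or that SAP 5.2.4 claims statistical significance. Neither follows, and Protocol 7.2.2 makes clear that the significance meant is clinical.
- *Other summaries are planned.* Total and subscale scores are summarised over time, so an average worsening would be visible. That helps, but it does not correct the responder proportion. The split by best response gives context but is not a control, since the groups may differ in number of looks.
- *The primary endpoint is also a best response during the study.* True, and it makes an ever-improved figure consistent with the plan's style. It does not remove the noise.

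**Conclusion.** The concern holds in direction. Read naturally, the planned proportion is biased upward by measurement noise, increases with the number of questionnaires, and can differ between the PR/CR and SD/PD groups merely because follow-up differs. This follows from the single baseline, the repeated assessments and the absence of confirmation. The lack of a control arm means the noise share cannot be subtracted.

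The amount is not established. With five visits and no true change, the any-time rate runs from about 3% to 55% as the assumed SD goes from 2 to 7, and correlation between visits lowers it. It exceeds the single-visit rate in every scenario tried. Whether the two response groups will in fact differ in number of looks is plausible from the follow-up rules but cannot be known from the plan.

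This is a worthwhile improvement to a secondary, descriptive summary. It does not undermine the study's formal results.

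**What to change.** In SAP 5.2.4, for the total summary score:

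1. Report the proportion improved and the proportion worsened by the 7-point threshold at every scheduled visit (Weeks 5, 13, 25, 37 and 49). For each visit show both the number with data and the All Treated denominator. Using only the second, with missing counted as not improved, would make late visits partly a measure of dropout and data cutoff. Using only the first would hide attrition.
2. Report the proportion improved at two consecutive scheduled visits.
3. Keep the any-time proportion, labelled as supplementary, and state that one qualifying score is enough.
4. Use one threshold throughout, either strictly more than 7 or 7 or more.

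All the data are already collected. The cost is a few more table rows and a lower headline proportion.
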